8.2.8. Investigational Product Adherence

This analysis will be based on the FAS1.

IP adherence (%) is monitored using the medication adherence monitoring platform for all participants in the study. The IP adherence is defined as the number of capsules taken, divided by the number of capsules planned to be taken, times 100. For participants that complete the treatment period the planned number of capsules taken is

- a) $(\text{Study Day of Day 28 visit} - \text{Day of the first dose} + 1)$, if Study Day of Day 28 visit is in 28 ± 2 window;
- b) 26, if Study Day of Day 28 visit < 26 ;
- c) 30, if Study Day of Day 28 visit > 30 .

For participants that discontinue the treatment early, the planned number of capsules is (Last Dose Date – First Dose Date + 1).

IP adherence will be summarized on Safety Set by treatment group. Number and percentage of participants with IP adherence in categories (<80%, 80-100%, >100%) will be provided. IP adherence will be listed.

8.3. Efficacy Analysis

8.3.1. Definition of Efficacy Variables

8.3.1.1. Primary Efficacy Assessment and Estimand

The main interest of the primary analysis in this trial is to estimate the baseline differences between participants with HD and HP in HD-CAB composite outcome. This is a comparison between two populations without establishing a treatment effect and without potential intercurrent events. Therefore, we will not present an explicit definition of an estimand in this analysis.

The HD-CAB is a cognitive assessment battery developed for HD patients by [Stout et al. \(2014\)](#). The HD-CAB will be assessed on Screening Period (Day -28 to -2), pre-dose on Day 1, post-dose on Day 14 and Day 28, and during follow-up on Day 42.

HD-CAB consists of 6 subtests and each variable will be used to calculate HD-CAB composite score as outlined in [Table 2](#). If at least 1 out of 6 HD-CAB subtests are missing, the HD-CAB composite score will be set to missing.

Table 2. HD-CAB Test Variables

Subtest Name (Assessment Type)	Cognitive Function Assessed	Variables	Score Range		Interpretation of Raw value	Recode
			Min.	Max.		
Symbol Digit Modalities Test (Paper)	Visuospatial attention, processing speed, working memory	Number of correctly coded items	0	110	High score indicates better performance	Not Needed; Use raw score
One Touch Stockings of Cambridge (Computer)	Planning, working memory	Mean time to reach a correct response (sec), averaged across all 10 trials	Not defined	Not defined	High score indicates worse performance	Part 1: Divide scores by 1000 to convert scores from milliseconds to seconds Part 2: Multiply scores by -1 so that higher values represent

Subtest Name (Assessment Type)	Cognitive Function Assessed	Variables	Score Range		Interpretation of Raw value	Recode
			Min.	Max.		
						better performance
Trail Making Test: Trail B (Paper)	Flexibility, visuospatial attention, psychomotor speed	Time (seconds) to complete the task	0 sec	240 sec	Higher value indicates worse performance	Multiply raw values by -1 so that higher values represent better performance
Hopkins Verbal Learning Test-Revised (Paper)	Verbal memory	Total correct recall trials over the 3 learning and 1 delayed recall trials	0	48	High score indicates better performance	Not Needed; Use raw score
Paced Tapping (Computer)	Timing, psychomotor coordination	The reciprocal of the standard deviation of the intertap intervals that occurred following cessation of the	Not defined	Not defined	Higher value indicates better performance	Not Needed; Use raw score

Subtest Name (Assessment Type)	Cognitive Function Assessed	Variables	Score Range		Interpretation of Raw value	Recode
			Min.	Max.		
		pacing tones over all trials taken (ms ⁻¹)				
Emotion Recognition (Computer)	Emotion recognition	Number of negative emotions correctly identified	0	24	High score indicates better performance	Not Needed; Use raw score

Computing HD-CAB composite scores involves following three steps. HD-CAB composite scores will be calculated per each visit per each baseline population sample mean as defined in the step 2.

Step 1: For Trail Making Test B and One Touch Stockings, reverse the score by multiplying by -1 to make higher scores indicate better performance across all the 6 subtests (See Recode column of Table 2)

Step 2: For each subtest, compute two z-scores for each participant using the formula:

$$z = \frac{\chi - \mu}{\sigma}$$

where χ is a participant's score, μ is a mean and σ is a standard deviation at baseline of

- (i) HD population sample when it is used for efficacy assessment between Sage-718 vs. placebo (if not otherwise is stated);
- (ii) Healthy population sample when it is used for the comparison of HP vs. participants with HD.

Step 3: To compute each participant's composite score, by calculating the average of six z-scores for each population sample mean.

The computation of exploratory cognitive batteries will be done as following:

- (i) Executive Function Focus Battery (EFFB) composite score will be calculated as an average of three z-scores of Symbol Digit Modalities Test (SDMT), Trail Making Test: Trail B (TMT B) and One Touch Stockings of Cambridge (OTS) for each population; If any individual subtest score is missing, the EFFT composite score will be set to missing.
- (ii) Reduced Motor Impact Battery (RMIB) composite score will be calculated as an average of three z-scores of OTS, Hopkins Verbal Learning Test-Revised (HVLT) and Emotion Recognition (ERT); If any individual subtest score is missing, the RMIB composite score will be set to missing.

Because the HD cohort in the study is relatively more progressed compared to the HD cohort in Stout et al. (2014), some participants may not be able to complete the TMT B test in the allotted 240 seconds (see more details in Appendix G). As such, we will explore the following approaches:

- (i) Calculate the outcome of TMT B test as

$$25 \cdot \frac{\text{Time}}{L},$$

where L is an order number of the last symbol reached in TMT B test and Time is the observed time of completion of TMT B.

The rational for this approach is to estimate the time to completion using the time needed to complete one symbol multiplied by the total number of symbols, which

is equal to 25. This calculated outcome of TMT B test will be recorded by multiplying by -1 so that higher values represent better performance.

(ii) Calculate the outcome of TMT B test as a speed of completion, which is the number of symbols done in 1 second as an outcome of TMT B test, and calculate it as

$$\frac{L}{Time},$$

where L is an order number of the last symbol reached in TMT B test and $Time$ is the observed time of completion of TMT B in seconds.

(iii) Consider only participants with baseline TMT B values < 240 seconds.

For all sensitivity analyses the calculation of HD-CAB and exploratory composite scores will be done accordingly.

8.3.1.1.1. HD-CAB Symbol Digit Modalities Test

The Symbol Digit Modalities Test is widely used to monitor changes in cognitive function over time and for early detection of cognitive dysfunction. The task requires participants to use a reference key to pair specific numbers with geometric figures. The number of correct pairings (out of 110 possible) achieved within 90 seconds is summed to generate a total score.

8.3.1.1.2. HD-CAB One Touch Stockings of Cambridge

One Touch Stockings of Cambridge is a computerized test of executive function. For this task, participants must imagine stacking a set of colored balls to match an example by moving 1 ball at a time into 1 of 2 possible locations. The goal is to perform the task using the smallest number of moves possible. The participant selects that number from the response options on the screen. The primary measure for analysis is time to 1st correct response.

8.3.1.1.3. HD-CAB Trail Making B

The Trail Making test is a speeded graphomotor test of visual attention and task switching, administered in two parts. Only part B will be used for primary analysis. Part B includes an additional set -switching component, requiring the examinee to connect a series of alternating numbers and letters in order from lowest to highest, as in 1-A-2-B-3-C..., in the shortest time possible. The primary measure for analysis is time to completion.

8.3.1.1.4. HD-CAB Hopkins Verbal Learning Test

The Hopkins Verbal Learning Test assessed is used to assess verbal learning and memory. The test consists of three learning trials over which a 12-item semantically categorized list is read aloud by an examiner. The examinee is asked to recall as many items as possible from memory immediately following each trial (immediate recall) and again following a delay (delayed recall). The learning list items are then presented among additional items that were not previously presented, and examinee is asked to identify which items were on the original list by responding yes/no to each item (recognition). The primary measure for analysis is the total

[figure not shown]
words correctly recalled over 4 trials (3 immediate and 1 delayed) with a maximum of 48 correct.

8.3.1.1.5. HD-CAB Paced Tapping Test

In paced tapping, examinees are presented with auditory pacing tones and instructed to harmonize their fingertaps with the pacing tones. A self-paced phase follows, in which the auditory pacing cue is removed, and ends with another auditory cue demarking the end of the test. The primary measure of analysis is paced tapping consistency, calculated as 1/SD of the intertap interval (1/msec).

8.3.1.1.6. HD-CAB Emotion Recognition Task

The Emotion Recognition Task has participants identify the emotions expressed on a series of computer-generated human faces (i.e., sadness, happiness, fear, anger, disgust, surprise). The responses can be analyzed by total errors, response latency, and the number of errors for each emotion. The primary measure for analysis is the number of correct negative emotion trials (out of 24).

A horizontal bar chart with 20 bins. The x-axis represents the value of each bin, and the y-axis represents the frequency or count of data points falling into each bin. The distribution is highly right-skewed, with the highest frequency in the first bin (approximately 1000) and a long tail extending to the right. The bins are represented by black horizontal bars.

Bin Range	Frequency
0-10	~1000
10-20	~100
20-30	~100
30-40	~100
40-50	~100
50-60	~100
60-70	~100
70-80	~100
80-90	~100
90-100	~100
100-110	~100
110-120	~100
120-130	~100
130-140	~100
140-150	~100
150-160	~100
160-170	~100
170-180	~100
180-190	~100
190-200	~100

A horizontal bar chart with 20 categories on the x-axis and 20 data points on the y-axis. The bars are black and vary in length, representing the value for each category. The categories are labeled with black numbers from 1 to 20. The data points are represented by black horizontal bars of varying lengths. The x-axis is labeled 'Category' and the y-axis is labeled 'Value'.

Category	Value
1	10
2	15
3	12
4	18
5	14
6	16
7	19
8	21
9	17
10	13
11	11
12	19
13	15
14	20
15	18
16	16
17	19
18	22
19	17
20	14

A series of horizontal black bars of varying lengths, likely representing data points or categories in a visualization. The bars are arranged in a grid-like structure, with some rows containing a single bar and others containing multiple bars. The lengths of the bars vary significantly, with some being very short and others being very long. The bars are positioned against a white background.

A series of horizontal black bars of varying lengths, likely representing data points or categories in a visualization. The bars are arranged in a grid-like structure, with some rows containing multiple bars and others containing a single bar. The lengths of the bars vary significantly, with some being very short and others being very long, suggesting a wide range of values or categories. The bars are set against a white background and are separated by small gaps.

A large number of black horizontal bars of varying lengths, likely representing data points or categories in a visualization. The bars are arranged in a grid-like pattern, with some bars having small black squares to their left. The lengths of the bars vary significantly, with some being very long and others very short. The overall effect is a dense, abstract pattern of horizontal lines.

A series of horizontal black bars of varying lengths, likely representing a redacted document or a visual representation of data. The bars are arranged vertically and vary in length, with some being very short and others being quite long, creating a pattern of horizontal lines.

A horizontal bar chart showing the distribution of 1000 samples across 10 categories. The x-axis represents the number of samples (0 to 1000) and the y-axis represents the category index (0 to 9). Categories 0, 1, 2, 3, 5, 6, 7, 8, and 9 have 1000 samples each. Category 4 has 500 samples. Category 4 is the only one with a tick mark on the y-axis.

Category	Number of Samples
0	1000
1	1000
2	1000
3	1000
4	500
5	1000
6	1000
7	1000
8	1000
9	1000

A large black rectangular redaction box covers the bottom portion of the slide content.

[REDACTED] [REDACTED]

[REDACTED]

For more information, contact the Office of the Vice President for Research and Economic Development at [contact] or [contact].

For more information, contact the Office of the Vice President for Research and Economic Development at [contact] or [contact].

[REDACTED]

© 2013 Pearson Education, Inc.

11. **What is the primary purpose of the *Journal of Clinical Oncology*?**

11. **What is the primary purpose of the *Journal of Clinical Endocrinology and Metabolism*?**

Black box for the final answer.

[REDACTED]	[REDACTED]

[figure not shown]
10

11 of 11

A horizontal bar chart consisting of 20 black bars of varying lengths. The bars are arranged in a single row, with the longest bar on the far left and the shortest on the far right. The bars are separated by small gaps.

8.3.1.2.5.3. National Sleep Foundation Sleep Diary

Once daily in the morning, participants will briefly answer 5 questions about sleep length, sleep latency, night awakenings, and sleep quality. These questions have been modified from version 6 of the National Sleep Foundation Sleep Diary (National Sleep Foundation). This diary will be completed each morning during the Treatment Period using a mobile device. At scheduled clinic visits, the task will be performed in the clinic under observation by study staff, otherwise the participant will perform this task remotely (at home). Sleep length will be calculated in minutes as a difference between participant get out of bed this morning and time participant went to bed last night if the participant went to sleep before the midnight, otherwise the difference will be before the out of bed time and the time when participant went to bed in this day. Mean sleep diary assessments will be derived based on study days for clinic visit days using the mean of non-missing assessments between the previous visit day (exclusive) and the current visit day (inclusive). The baseline sleep diary measurement will be calculated as the mean of days immediately preceding the first dose day time. The precision level of averages to keep one decimal place. Refer to Table 3 above for the visit derivation.

A horizontal bar chart with 10 categories on the y-axis and a scale from 0 to 1000 on the x-axis. The bars are black and show the following approximate values for each category:

Category	Approximate Value
0	100
1	100
2	100
3	100
4	100
5	100
6	100
7	100
8	100
9	100

A large grid of 100 horizontal bars, each consisting of a short black segment on the left and a long black segment on the right. The bars are arranged in a grid pattern.

A horizontal bar chart consisting of 20 bars. The bars are black and are arranged in a single row. The lengths of the bars increase from left to right, with a significant gap between the 10th and 11th bars. The bars are of varying lengths, with the 11th bar being the longest and the 10th bar being the shortest.

8.3.2. Visit Windows for Efficacy Analyses

The scheduled visits will not be windowed and will be used at nominal visit value for treatment period (Days 14, 28, and 42). Unscheduled and ET visit will be mapped to a scheduled visit for analysis. Unscheduled measurements and early termination visit will be included only if a scheduled measurement is not available, and if the unscheduled measurement falls within the visit window or the scheduled visit. If there are two or more measurements in a visit window, the measurement taken closest to the study day target will be used in analysis. If the two have same distance from the target study day, the latter one will be used.

Table 4. Analysis Visit Windows for HD-CAB

Scheduled Visit	Study Day of Expected Visit	Study Day Window for Visit
Baseline	1	≤ 1
Day 14 (± 2 days)	14	2 to 20
Day 28 (± 2 days)	28	21 to 35
Day 42 (± 2 days)	42	≥ 36

8.3.3. Analysis of Primary Outcome

The FAS will be used for primary summary tables. All participants who have baseline measures will be analyzed.

8.3.3.1. Primary Analysis

The primary efficacy endpoint is the difference between participants with HD and HP in baseline measures of the HD-CAB composite z-score standardized using mean and standard deviation from healthy participants. This primary endpoint will be analyzed using T-test. The mean difference, its standard error (SE) and 95% confidence interval (CI) and corresponding p-value will be reported.

A scatterplot showing the composite scores in two cohorts with mean \pm standard error of the mean (SEM) bars and a boxplot comparing the distribution in two groups will be provided.

[figure not shown]

8.3.4.4. Sleep Diary

A summary of sleep diary and sleep length will be presented using descriptive statistics.

A series of horizontal black bars of varying lengths, likely representing redacted text or data. The bars are positioned in a grid-like pattern, with some bars being significantly longer than others, suggesting a list or table where certain entries are obscured.

[REDACTED]

8.4. Safety Analysis

Safety and tolerability of SAGE-718 is a secondary objective of this study. The incidence of adverse events/serious adverse events, and changes in vital signs and clinical laboratory parameters are secondary endpoints, change from baseline in electrocardiograms and responses on the Columbia-Suicide Severity Rating Scale are the other endpoints (Table 8). All safety analysis will be performed on the Safety Set using actual treatment received.

The safety endpoints evaluated at scheduled visits within treatment period are taken as done in nominal visit, without any windowing. If a value is available for a nominal scheduled visit, that value will be used in summary by visit. If scheduled visit value is not available, a value from the specific visit window will be included in summary. For Post-treatment period visits, the choice of the visit will follow the same rule as described in Table 9, Table 10 and Table 11.

Anytime on treatment, last value on treatment and last value on study will be included in the summaries whenever indicated in the relevant sections below. Anytime on treatment is defined as measurement on or after first dose, on or before last dose. Last value on treatment is defined as the last post-baseline value between first dose of IP (exclusive) and up to last dose of IP (inclusive). Last value on study is defined as the last post-baseline value after the first dose of IP.

No statistical hypothesis testing will be conducted on the safety analyses.

Table 8. Summary of Safety Endpoints

Safety Evaluation	Incidence	Raw Value	Change from Baseline	Normal Range Shift from Baseline	Potentially Clinically Significant	Abnormality/ Clinical Significance
Adverse Events	X					
Clinical Laboratory		X*	X	X	X	*
Physical Exam		*				
Vital Signs		X*	X		X	
ECG		X*	X		X	*
C-SSRS		X*		X		

Safety Evaluation	Incidence	Raw Value	Change from Baseline	Normal Range Shift from Baseline	Potentially Clinically Significant	Abnormality/ Clinical Significance

ECG = Electrocardiograms; C-SSRS = Columbia–Suicide Severity Rating Scale X = value will be summarized in tables * = value will be listed in individual participant data listings
						

For safety analysis, unscheduled measurements will be included only if a scheduled measurement is not available, and the unscheduled measurement falls within the visit window for the scheduled visit (Table 9, Table 10 and Table 11). If there are two or more measurements in a visit window, the measurement taken closest to the study day target will be used in analysis. If the two have same distance from the target study day, the latter one will be used.

Table 9. Analysis Visit Windows for C-SSRS

Scheduled Visit	Study Day of Expected Visit	Study Day Window for Visit
Baseline	1	≤1
Day 14 (±2 days)	14	2 to 20
Day 28 (±2 days)	28	21 to 35
Day 42 (±2 days)	42	≥36

Table 10. Analysis Visit Windows for Vital Signs

Scheduled Visit	Study Day of Expected Visit	Study Day Window for Visit
Baseline	-1	≤1
Day 14 (±2 days)	14	2 to 20
Day 28 (±2 days)	28	21 to 35
Day 42 (±2 days)	42	≥36

Table 11. Analysis Visit Windows for Clinical Laboratory and ECG

Scheduled Visit	Study Day of Expected Visit	Study Day Window for Visit
Baseline	-1	≤1
Day 28 (±2 days)	28	2 to 35
Day 42 (±2 days)	42	≥36

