8.4.2. Clinical Lab

Clinical laboratory assessments will include blood samples for hematology, clinical chemistry, coagulations, and urinalysis. Samples will be collected ≤ 2 hours prior to dosing on dosing days. On non dosing days, collection may occur at any time.

The actual results as collected will be displayed in the listings.

All laboratory values will be summarized for the Safety Set using actual treatment received. Results of continuous hematology, clinical chemistry parameters, coagulation, and urinalysis parameters (quantitative) at each scheduled visit and mean changes from baseline will be summarized using standard international (SI) units. In addition, it will also include the summary of last post-baseline value on treatment (on or after first dose, on or before last dose) and on study (on or after first dose, on or before last day of the study).

All laboratory results will be listed in individual participant data listings.

Normal ranges for each parameter will be provided by the central laboratory. Shift from baseline to worst post-baseline values at any time on treatment, and shift from baseline to the last value on treatment (on or after first dose, on or before last dose) and the last value on study (on or after first dose, on or before last day of the study) in abnormality of results will be summarized. If a participant has both low and high post-baseline records, the participant will be counted twice for each low and high cell.

The number and percentage of participants with potentially clinically significant (PCS) values will be provided in separate displays in hematology, clinical chemistry and liver function tests provided for such occurrence for anytime on treatment, last value on treatment, after the last dose of treatment (follow-up period). PCS values will be identified for specific laboratory parameters as outlined in Table 12.

Liver function tests will be monitored closely for PCS values, and will be summarized for occurrence anytime post-baseline for the following parameters for these PCS threshold (for condition involving more than one parameter, the results need to be from the same timepoint):

- Alanine Aminotransferase: $>3\times\text{ULN}$, $>5\times\text{ULN}$, $>10\times\text{ULN}$
- Aspartate Aminotransferase: $>3\times\text{ULN}$, $>5\times\text{ULN}$, $>10\times\text{ULN}$
- Alanine Aminotransferase or Aspartate Aminotransferase: $>3\times\text{ULN}$, $>5\times\text{ULN}$, $>10\times\text{ULN}$

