A single 12-lead ECG under Protocol Amendment 1 and 2 and triplicate 12-lead ECG under Original Protocol will be performed after the participant has been resting in the supine position for at least 5 minutes. If the multiple 12-lead ECG are performed, the average of all values on the same date will be used in the summary. If there are both scheduled visit and unscheduled visit on the same date, all the assessments on that date are considered as the scheduled visit for the summary. A summary of the observed values (raw values for the single ECG; average values for the multiple ECG on the same date) and change from baseline values will be summarized by each scheduled visit for the following ECG parameters: heart rate, PR, QRS, QT, and QT corrected according to Fridericia's formula (QTcF) interval. This summary will also include the last values on treatment and on study. A by-participant listing of 12 lead ECG will also be provided for each of the ECG measurements.

Each ECG is evaluated as 'normal', 'abnormal, not clinically significant' and 'abnormal, clinically significant'. The number and percentage of participants with the categories of 'abnormal, clinically significant' and 'abnormal, not clinically significant' from the latest triplicated ECG value will be provided at baseline and each post-baseline scheduled assessment time point.

Potentially clinically significant values of QTcF as outlined in Table 13 will be summarized by treatment for anytime on treatment, last value on treatment, after the last dose of treatment (follow-up period). Electrocardiogram findings will be listed by participant and visit.

Table 13. Potentially Clinically Significant Values for 12-Lead ECG Parameters

12-Lead ECG	Units	Criteria for PCS Values (Observed values)		Criteria for PCSC values (Change from Baseline)	
		High	Low	Increase	Decrease
QTcF	msec	>450 but ≤480 >480 but ≤500 >500	NA	≥30 to 60 >60	NA

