11. LIST OF APPENDICES

APPENDIX A. SCHEDULE OF ASSESSMENTS – HUNTINGTON’S DISEASE

Assessments	Screening Period		Treatment Period			Follow-up Day 42 (±2 days) or ET
	Days -28 to -2	Day-1	Day 1	Day 14 (±2 days)	Day 28 (±2 days)	
Informed consent ^a	X					
Inclusion/exclusion criteria	X	X	X			
Randomization ^b			X			
Family/medical history and demographics ^c	X					
Participant training ^d	X	X	X			
Body weight	X				X	X
Body height	X					
Vital signs (including orthostatics) ^e	X	X		X	X	X
Physical examination ^f	X	X			X	X
CAG test (if not collected as part of medical history) ^g	X					
FSH test ^h	X					
Serology test ⁱ	X					
12-lead ECG ^j	X	X			X	X
Clinical laboratory assessments ^k	X	X			X	X
Urine drug test ^l	X	X	X	X	X	X
Alcohol test ^l	X	X	X	X	X	X
Cigarette/tobacco use assessment ^m	X		X	X	X	X
Pregnancy test ⁿ	X		X		X	X
C-SSRS (Screening)	X					
C-SSRS (since last visit)			X	X	X	X

Assessments	Screening Period		Treatment Period			Follow-up
	Days -28 to -2	Day-1	Day 1	Day 14 (±2 days)	Day 28 (±2 days)	Day 42 (±2 days) or ET
Cognitive test (HD-CAB) ^t	X		X	X	X	X
Daily Mobile Assessments ^x		X-----X				
IP self-administration ^y			X (once daily in the morning)			
IP dispensation ^z		X	X			
IP accountability/return ^{aa}				X	X	
AEs/SAEs			X (from time of ICF throughout the duration of participation)			
Prior and concomitant medications	X-----X					

Abbreviations: AE = adverse event; CAP = CAG-Age-Product; [REDACTED]

[REDACTED] COVID-19 = coronavirus disease 2019;

C-SSRS = Columbia–Suicide Severity Rating Scale; [REDACTED]

[REDACTED] ECG = electrocardiogram; ET = early termination; FSH = follicle-stimulating hormone; HD = Huntington's Disease; HD-CAB = Huntington's Disease Cognitive Assessment Battery; [REDACTED]

[REDACTED] HIV = human immunodeficiency virus; ICF = informed consent form; IP = investigational product; [REDACTED] O = optional; [REDACTED]

SAE = serious adverse event; [REDACTED]

a. Both participants and study partners (if applicable) will be consented during the Screening Period.

Note: On screening (Days -28 to -2), Day 28, and Day 42, safety assessments [REDACTED] [REDACTED] may be done on separate day(s) than the cognitive assessments, if need be, provided that all assessments are completed within the specified visit window (± 2 days).

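### Lab and QTcF abnormalities have no any-time-post-baseline display, and HD participants who stop IP before the Day 28 visit will normally be missing from the on-treatment ones

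*SAP*

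**What the plan says.** **On-treatment period.** SAP 8.4 sets it for safety measurements: "Anytime on treatment is defined as measurement on or after first dose, on or before last dose". The last value on treatment has the same end point: "the last post-baseline value between first dose of IP (exclusive) and up to last dose of IP (inclusive".

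**Displays that use it.**
- Lab shifts (SAP 8.4.2): "Shift from baseline to worst post-baseline values at any time on treatment", plus shifts to the last value on treatment and to the last value on study.
- Lab PCS counts (SAP 8.4.2): "provided for such occurrence for anytime on treatment, last value on treatment, after the last dose of treatment (follow-up period").
- QTcF PCS counts (SAP 8.4.3): "will be summarized by treatment for anytime on treatment, last value on treatment, after the last dose of treatment (follow-up period").

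**The exception.** A further liver display with several thresholds is not cut at the last dose: "Liver function tests will be monitored closely for PCS values, and will be summarized for occurrence anytime post-baseline".

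**Schedule.** In SAP Appendix A and Protocol Table 1, the row "Clinical laboratory assessments" and the 12-lead ECG row are marked for HD participants at Screening, Day -1, Day 28 and Day 42/ET. Neither is marked at Day 14. The window table ("Table 11. Analysis Visit Windows for Clinical Laboratory and ECG") agrees: its post-baseline rows are Day 28 (study days 2 to 35) and Day 42 (day 36 onward). Vital signs and C-SSRS do have a Day 14 row.

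**After early stopping.** SAP 5.1 asks HD participants who stop IP early to attend the remaining visits. Those who leave the study are asked for an ET visit.

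**The concern.** An on-treatment period that closes at the last dose works well when tests are frequent. Here the only scheduled test during dosing comes at the end of the 28 days. A participant who stops on Day 10 is next tested at an ET visit or at Day 28, and normally both fall after the on-treatment period has closed.

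The on-treatment lab and QTcF displays therefore mainly describe participants who stayed on IP to the Day 28 visit. If some people stop because they tolerate the drug poorly, they are the ones missing. Changes in laboratory parameters are a secondary endpoint and ECG change is another stated safety endpoint. With about 20 participants per arm, one or two people can change what a table shows.

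**Working it through.** **1. The plan's own figure.** The only stated number near this point is the dropout allowance in SAP 5.2: 32 evaluable / (1 - 0.20) = 40 randomized, or 20 per arm. It reproduces exactly. Evaluable there means IP received, a valid baseline and at least one postbaseline efficacy assessment. The 20% is thus an allowance for non-evaluability, not a rate of stopping IP. Someone who stops on Day 20 after Day 14 testing is evaluable, yet is affected here.

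**2. Which last-dose days leave no on-treatment test.** Let d be the study day of the last dose and v the day of the test. A test counts if v ≤ d. Permitted days are 26 to 30 for the Day 28 visit and 40 to 44 for the Day 42 visit (± 2 days).

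| Last dose (d) | Day 28 visit days that count | Day 42 visit days that count |
|---|---|---|
| 1 to 25 | none | none |
| 26 | 26 | none |
| 27 | 26, 27 | none |

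For d = 26 or 27, a test counts only if the Day 28 visit had already been held, which is effectively completion. Completers' Day 28 tests do count: the Protocol Table 1 footnote on IP self-administration puts safety assessments before that day's supervised dose.

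**3. Exceptions.**
- An ET visit on the last-dose date can count. Protocol 8.4.2 links withdrawal, the ET visit and the end of IP. The SAP does not say whether date or time decides for labs and ECGs.
- An unscheduled test while still dosing could count. SAP 8.4 uses unscheduled values only when no scheduled value is available, and does not say whether that rule governs the any-time tables.

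**4. Where the values of a participant with d = 10 go, if tested at Day 28 and Day 42.**

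| Display | Included? |
|---|---|
| Lab worst-value shift | No |
| Lab or ECG last value on treatment | No |
| On-treatment PCS, labs and QTcF | No |
| After-last-dose PCS, labs and QTcF | Yes |
| Last value on study (and lab shift) | Day 42 value only |
| Day 28 and Day 42 by-visit summaries | Yes |
| Liver thresholds, any time post-baseline | Yes |
| Listings | Yes |

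If a lab value is abnormal at Day 28 and normal at Day 42, the worst-value shift omits the participant and the last-on-study shift shows normal. The abnormality is in neither.

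**5. Size.** The stopping rate r is an assumption. Affected = 40 × r; on-treatment denominator per arm = 20 × (1 - r), with equal stopping in both arms.

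| r | Affected of 40 | Denominator per arm |
|---|---|---|
| 5% | 2 | 19 |
| 10% | 4 | 18 |
| 20% | 8 | 16 |
| 30% | 12 | 14 |

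**6. Hypothetical arm of 20 with 4 early stoppers.** Suppose 2 of the 4 have a PCS value after stopping and no completer does. On treatment reads 0/16 = 0%. After last dose reads 2/20 = 10%. Any time post-baseline would also read 2/20 = 10%, so here the after-last-dose display already shows the signal. Now suppose one completer also has a PCS value at Day 28 that resolves by Day 42. On treatment reads 1/16, after last dose reads 2/20, and neither gives the 3/20 = 15% who ever had one.

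**The case against.** The strongest reply is that nothing disappears. An early stopper's values enter the after-last-dose PCS display, the last-value-on-study summaries, the by-visit tables and the listings. When the ET visit is the last assessment, its lab value is the last value on study and so enters a lab shift table. Labs judged clinically significant by the investigator become adverse events, and SAP 8.4.1 counts on-treatment events up to 30 days after the last dose. Percentages use participants with data (SAP 8.1), so a smaller denominator would be visible. Safety is descriptive, with no hypothesis tests. All of this stands, and it narrows the point to a missing combined display.

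A reader might infer more than the documents support:
- **That 8 of 40 would be affected.** This treats the evaluability allowance as a stopping rate. It bounds the number in neither direction.
- **That these tables are biased toward no drug effect.** This needs stopping to be related to tolerability and to differ by arm. The documents give no rate for either arm, and it would concern only the on-treatment displays.
- **That ECGs lose a worst-value shift.** None is planned: SAP Table 8 marks no normal-range shift for ECG. The ECG effect is on QTcF PCS counts and last-value-on-treatment summaries.
- **That the Day 28 window contradicts the on-treatment rule.** Visit and exposure period are different classifications. An off-drug value at Day 28 can properly be both a Day 28 value and an after-last-dose value.

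**Conclusion.** The point holds as a gap in the planned displays. With a last dose on Days 1 to 25, a participant normally has no scheduled on-treatment lab or ECG value and is absent from the lab worst-value shift and the on-treatment PCS counts for non-liver labs and QTcF. The on-treatment and after-last-dose counts cannot simply be added, because one person can appear in both. The liver thresholds show that the SAP already has the rule that would close the gap.

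The number affected rests on an assumed rate of early IP stopping: 2 to 12 of 40 at 5% to 30%. It is zero if nobody stops before the Day 28 visit, and smaller if same-day ET visits or unscheduled on-treatment tests are counted. The primary endpoint is untouched, because it is a baseline comparison. This is a modest change worth making, not a sign that safety data are hidden.

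**What to change.** In SAP 8.4.2, add a lab shift from baseline to the worst value at any time post-baseline, meaning after the first dose through the last study visit. In SAP 8.4.2 and 8.4.3, add an any-time-post-baseline PCS count for all labs and for QTcF. State that unscheduled values count in these displays, and whether date or time decides when a test and the last dose fall on the same day.

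Keep the on-treatment and follow-up displays as they are. Do not move off-drug values into a treatment-period column. For a last dose on Day 10, the Day 28 test is 28 - 10 = 18 days off drug, longer than the roughly 42 - 28 = 14 days for a completer at Day 42. Calling it a treatment-period value could dilute a reversible effect.

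The cost is SAP wording and table programming, with no new data. The small downside is that the added display mixes on-drug and off-drug values; a flag giving days since the last dose deals with that. Participants with no post-baseline test at all would still be missing, so the table should give their number. If the database is already locked, SAP Section 2 requires the change to be documented in the clinical study report.
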